5.2.3 Visits 3 and 4/Days 8 and 15 (QD Treatment)

These visits must occur within the following visit windows:

- Visit 3/Day 8: 7 days (±4 days) after Visit 2
- Visit 4/Day 15: 14 days (±4 days) after Visit 2.

Subjects should not apply the study medication within 18 hours prior to these study visits.

At these visits, the investigator or designee will perform the following procedures:

- 1. Query the subject in a non-directive manner about any changes in her/his health since the previous visit and report all AEs as appropriate
- 2. Query the subject about any changes in her/his concomitant therapies since the previous visit and report changes as appropriate
- 3. Confirm the subject has followed all study instructions
- 4. Confirm the location of each Target cNF Tumor
- 5. Have the subject perform an LTA of the symptoms for each Target cNF Tumor
- 6. The investigator will perform an LTA of the signs for each Target cNF Tumor
- 7. Collect and weigh study medication
- 8. Weigh and dispense study medication
- 9. Review the study instructions with the subject
- 10. Schedule the next study visit.

5.2.4 Visit 5/Day 29 (End of Treatment; start of no treatment follow-up)

This visit must occur 28 days (± 4 days) after Visit 2.

At selects sites performing PK sample collection at this visit:

- Subjects will be confined at the investigational center for approximately 6 hours for the collection of PK blood samples and for excision of the 6 Study cNF Tumors
- This visit must be scheduled so that the previous study medication application was completed 24 (±6) hours prior to the 0-hour PK blood sample.

At sites NOT performing PK sample collection at this visit: subjects will be confined at the investigational center for approximately 6 hours for excision of the 6 Study cNF Tumors.

At this visit, the investigator or designee will perform the following procedures:

- 1. Query the subject in a non-directive manner about any changes in her/his health since the previous visit and report all AEs as appropriate
- 2. Query the subject about any changes in her/his concomitant therapies since the previous visit and report changes as appropriate
- 3. Confirm the subject has followed all study instructions including, at select sites, appropriate timing of the previous study medication application for PK blood sampling
- 4. Measure vital signs
- 5. Perform a urine pregnancy test for WOCBP
- 6. Confirm the location of the 6 Study cNF Tumors (5 Target cNF Tumors and 1 Untreated cNF Tumor)
- 7. Measure the dimensions of each Target cNF Tumor
- 8. Have the subject perform an SSA for each Target cNF Tumor
- 9. Have the subject perform an LTA of the symptoms for each Target cNF Tumor
- 10. Perform a PTA for each Target cNF Tumor
- 11. The investigator will perform an LTA of the signs for each Target cNF Tumor
- 12. At select sites: Perform an ultrasound of each Target cNF Tumor
- 13. Take standardized color photographs of each Target cNF Tumor
- 14. Perform an ECG
- 15. Collect samples for clinical laboratory tests then conduct the appropriate activities as indicated below.

At select sites performing PK sample collection at this visit:

- 16. Collect 0-hour blood sample for PK analysis 24 (±6) hours after the previous study medication application and prior to the Visit 5 study medication application
- 17. Have the subject perform the last study medication application and record the Application Completion Time
- 18. Have the subject perform a post-application LTA of the symptoms for each Target cNF Tumor 10 (±4) minutes after the Application Completion Time
- 19. The investigator will perform a post-application LTA of the signs for each Target cNF Tumor 20 (±4) minutes after the Application Completion Time
- 20. Collect post-application blood samples for PK analysis
- 21. 4 (±1) hours after the Application Completion Time excise the 6 Study cNF Tumors (5 Target cNF Tumors and 1 Untreated cNF Tumor)
- 22. Collect and weigh study medication
- 23. Review the study instructions with the subject
- 24. Schedule Visit 6.

At sites NOT performing PK sample collection at this visit:

- 16. Have the subject perform the last study medication application
- 17. Have the subject perform a post-application LTA of the symptoms for each Target cNF Tumor 10 (±4) minutes after the Application Completion Time
- 18. The investigator will perform a post-application LTA of the signs for each Target cNF Tumor 20 (±4) minutes after the Application Completion Time
- 19. 4 (±1) hours after the Application Completion Time excise the 6 Study cNF Tumors (5 Target cNF Tumors and 1 Untreated cNF Tumor)

Date: 24-JUL-2020 Page 42 of 78 Supersedes: NEW

- 20. Collect and weigh study medication
- 21. Review the study instructions with the subject
- 22. Schedule Visit 6.

5.2.5 Visit $6/Day \ge 36$ to ≤ 50 (Excision wound care)

This visit must occur 7 (± 4) days after Visit 5 and 7 (± 4) days prior to Visit 7.

At this visit, the investigator or designee will perform the following procedures:

- 1. Query the subject in a non-directive manner about any changes in her/his health since the previous visit and report any changes as medical history or report as an AE as appropriate
- 2. Query the subject about any changes in her/his concomitant therapies since the previous visit and report changes as appropriate
- 3. Confirm the subject has followed all study instructions
- 4. The investigator will manage the excision wounds per her/his standard of care
- 5. Review the study instructions with the subject
- 6. Schedule Visit 7.

5.2.6 Visit 7/Day 57 (End of study, early termination)

This visit must occur 56 days (± 4 days) after Visit 2 and 7 (± 4) days after Visit 6.

At this visit, the investigator or designee will perform the following procedures:

- 1. Query the subject in a non-directive manner about any changes in her/his health since the previous visit and report all AEs as appropriate
- 2. Query the subject about any changes in her/his concomitant therapies since the previous visit and report changes as appropriate
- 3. Confirm the subject has followed all study instructions
- 4. Measure vital signs
- 5. Discharge the subject from the study.

5.3 Study cNF tumor identification

At Visit 1 the investigator will identify 6 Study cNF Tumors:

- 5 Target cNF Tumors with 1 tumor on the face and 4 tumors on the anterior trunk or upper extremities
- 1 Untreated cNF Tumor on the anterior trunk or upper extremities

The Untreated cNF Tumor should be located as far as possible from the nearest Target cNF Tumor. The Untreated cNF Tumor will NOT receive any study medication applications.

Date: 24-JUL-2020 Page 43 of 78 Supersedes: NEW

For this study the anterior trunk, upper extremities and face are defined as follows:

[figure not shown]
- Anterior trunk:
 - o The front of the torso, excluding the neck, down to the beltline
- Upper extremities:
 - o Arms from the shoulders to the tips of the fingers, including the back of the hands but excluding the palms
- Face (Target cNF Tumor #5 must be on the face):
 - Vertically from the mandibular ridge to the hairline (for subjects with a receding hair the hairline is defined by a vertical lie drawn coronally from tragus to tragus)
 - o Horizontally from tragus to tragus, excluding the eyelids and areas within 5mm of the orbital rim.

At Visit 1 each of the 6 Study cNF Tumors must meet the following criteria for the subject to be enrolled and at Visit 2 the 5 Target cNF Tumors must meet to the following criteria for the subject to be randomized:

- Has, in the investigator's opinion, a clinically typical appearance
- Is dome shaped
- Is not pedunculated
- Is a discrete tumor
- Is not irritated
- Is not in an area subject to repeated trauma (*e.g.*, area that is shaved, on the beltline, under a bra strap, etc.)
- Does not have an active cutaneous infection
- Has a diameter that is ≥ 5 mm and ≤ 10 mm
- Has a height of ≥2mm
- Is, when centered in the center of the provided template, the only cNF tumor visible
- Is not within 5mm of the orbital rim.

At Visits 1, the investigator and an investigational center staff member will identify the 6 Study cNF Tumors using the provided template.

Number the Target cNF Tumors starting with 1 proceeding up to 5 with no number omitted or reused. Identify the Untreated cNF Tumor with the designation "UT". For identification in the study photographs place 2 appropriately colored Identification (ID) Stickers in the small template cutouts approximately 180 degrees opposite each other with the Study cNF Tumor centered in large circular template cutout (diagram not to scale):

Write the Study cNF Tumor Identifier on one of the ID stickers.

The Study cNF Tumor Identifier/ID sticker color relationships are:

- Target cNF Tumor #1/white ID stickers
- Target cNF Tumor #2/red ID stickers
- Target cNF Tumor #3/yellow ID stickers
- Target cNF Tumor #4/blue ID stickers
- Target cNF Tumor #5/green ID stickers (Target cNF Tumor #5 must be on the face)
- Untreated cNF Tumor "UT"/pink ID stickers.

Both ID stickers must be visible in the Study cNF Tumor photographs.

At Visit 1 the investigator will use body charts and the photographs to document the location of each Study cNF Tumor. The investigator will record the location of each Study cNF Tumor on an appropriate body chart using the following process:

- Make a circle identifying the location of each Study cNF Tumor
- Write the Study cNF Tumor Identifier adjacent to the circle
- Record at least the following information on each body chart:
 - o Protocol number
 - o Subject Identifier
 - o Visit number.

At Visit 1, the investigator or designee will dispense a photocopy of the body charts completed at the visit to the subject as part of the subject instructions. The investigator or designee will place the original Visit 1 body chart in the subject's study file for use at Visit 2. The investigator or designee must also mark the approximate location of each Study cNF Tumor identified at Visit 1 in the CRFs and include the Study cNF Tumor Identifier.

At Visit 2, the investigator will use the Visit 1 body charts and photographs to identify the location of the 6 Study cNF Tumors.

Between Visit 1 and Visit 2 the status of 1 or more Target cNF Tumor may change, therefore at Visit 2, the investigator will evaluate each subject to determine which of the following categories describe each Target cNF Tumor identified at Visit 1:

- All 5 Target cNF Tumors meet the protocol requirements for the subject to be eligible for randomization
- 1 or more Target cNF Tumors do not meet the protocol requirements for the subject to be eligible for randomization, but the subject **HAS** sufficient additional cNF tumors that meet the requirements to provide 5 Target cNF Tumors for randomization (Note: 1 Target cNF Tumor must be on the face and 4 Target cNF Tumors must be on the anterior trunk or upper extremities)
- 1 or more Target cNF Tumor does not meet the protocol requirements for the subject to be eligible for randomization, and the subject **DOES NOT HAVE** sufficient additional cNF tumors that meet the requirements to provide 5 Target cNF Tumors for randomization.

At Visit 2, the investigator will discharge subjects from the study who are in category 3.

At Visit 2, for subjects who are in category 1 or 2 the investigator will follow the Visit 1

Date: 24-JUL-2020 Page 46 of 78 Supersedes: NEW

procedures to identify the 5 Target cNF Tumors to be treated and the 1 Untreated cNF Tumor. The investigator will use a new set of body charts to document the location of each Study cNF Tumor. The investigator will record the location of each Study cNF Tumor on an appropriate body chart using the following process:

- Make a circle identifying the location of each Study cNF Tumor
- Write the Study cNF Tumor Identifier adjacent to the circle
- Record at least the following information on each body chart:
 - o Protocol number
 - o Subject Identifier
 - Visit number.

At Visit 2, the investigator or designee will collect the body charts dispensed to the subject at Visit 1 and then dispense a copy of the body charts created at Visit 2 to the subject as part of the subject instruction review.

Clearly identify the Untreated cNF Tumor on the body chart and to the subject to ensure the subject understands the Untreated cNF Tumor is not to be treated with the study medication.

The investigator or designee will place the original Visit 2 body chart in the subject's study file for use at subsequent visits.

The investigator or designee must also mark the approximate location of each Study cNF Tumor (5 Target cNF Tumors and 1 Untreated cNF Tumor) in the CRFs and include the Study cNF Tumor Identifier.

At Visit 2-5, prior to any Target cNF Tumor assessments, an investigational center staff member other than the evaluating investigator will use the appropriate body charts and study photographs to identify the location each Target cNF Tumor for the study evaluations. The staff member will use the tumor template and for each Target cNF Tumor center the tumor in the large circular cutout and place the 2 appropriately colored and numbered ID stickers on the subject's skin.

At Visit 5 only, the staff member will mark the location of the Untreated cNF Tumor as described above to assist the investigator with excision.

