4.10 Subject instructions

At Visit 1, an investigational center staff member will dispense a Subject Instruction sheet to each subject.

During the entire duration of the study subjects must:

- Continue to use her/his routine cleansers and cosmetics
- Not apply any non-study topical products to any Target cNF within 18 hours prior to a study visit
- Avoid exposing each Target cNF to excessive natural (e.g., sunlight) or artificial (e.g., tanning beds) ultraviolet radiation and use her/his routine sunscreen if excessive exposure cannot be avoided
- Bring the subject instruction sheet to every visit.

During the 4-week treatment period, subjects must:

- Apply the study medication to each Target cNF as directed, once daily, with 24 (±6) hours between applications
- Not apply the study medication to any open wounds or obviously infected skin
- For Visits 3 and 4 do not apply the study medication within 18 hours prior to the visit
- Prior to Visit 5 perform the study medication application 24 (±6) hours prior to the visit
- Not wash or submerge a Target cNF Tumor for at least 6 hours after a study medication application
- Not apply any topical products to a Target cNF for at least 6 hours after a study medication application
- Not allow anyone else to use your study medication
- Keep the study medication away from children
- Store the study medication at room temperature
- Bring all study medication tubes to every visit
- Bring the subject instruction sheet to every visit.

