4.12.8 Study medication application

The study medications are for external, topical use on each Target cNF Tumor only and on the appropriate study subject only.

To perform a study medication application the subject should:

- Wash her/his hands before starting the application
- Avoid applying the study medication any open wounds or obviously infected skin
- Apply an amount of the assigned study medication sufficient to cover each Target cNF with a thin layer of the medication
- Gently rub in the study medication until no visible accumulation is evident
- Wash her/his hands after completing the application

The subject must apply study medication to the entire area of each Target cNF Tumor limiting exposure to the un-affected skin surrounding the tumor.

At Visit 2, an investigational center staff member will instruct the subject on the proper application technique. The staff member will observe the subject's study medication application to ensure proper application technique and record the time the subject completes the application to the last Target cNF Tumor as the Application Completion Time. The staff member will monitor the subject for adverse events for at least 20 minutes after the Application Completion Time. The subjects are to continue QD application of the assigned study medication to each Target cNF Tumor for 4 weeks with 24 (±6) hours between applications.

At Visit 5, the study medication application will be performed by the subject as part of the visit procedures at the investigational center. Record the time the subject completes the application to the last Target cNF Tumor as the Application Completion Time. The study medication tubes will be collected after the application at this visit.

For Visits 3 and 4 subjects should not apply the study medication within 18 hours prior to the study visit.

Prior to Visit 5 subjects must be instructed to perform the study medication application 24 (±6) hours prior to the visit.

After completing a study medication application, a subject should not:

- Wash or submerse any Target cNF Tumor for at least 6 hours
- Apply any topical products (*e.g.*, cosmetics, emollient/moisturizer, sunscreens) to any Target cNF Tumor for at least 6 hours.

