6.3.3 Study cNF Tumor excision for p-ERK levels

At Visit 5, 4 (±1) hours after the Application Completion Time for the last study medication application, the investigator will excise all 6 Study cNF Tumors (5 Target cNF Tumors and 1 Untreated cNF Tumor) to provide tissue samples to assess for p-ERK levels.

For each of the 6 Study cNF Tumors the investigator will shave excise the entire tumor and cut the tissue into 2 halves vertically ensuring that each half contains epidermis and dermis. Half the tissue sample will be immediately frozen, and half will be preserved in formalin following the instructions below:

- Frozen sample:
 - o Immediately freeze half the tissue in liquid nitrogen using forceps to immerse tissue in liquid nitrogen for ∼10 seconds
 - o Place the frozen tissue in a 2mL screw cap cryovial
 - o Immediately freeze on dry ice
 - Store the sample at -80°C until shipment.

• Formalin preserved sample:

O Within 30 minutes transfer half the tissue to a container prefilled with 10%

neutral-buffered formalin

• Store at room temperature until shipment.

The tissue forceps, cryovials and prefilled containers of formalin will be supplied to each

investigational center.

Each sample will be shipped to a NFlection selected laboratory for evaluation of p-ERK

levels. Detailed instructions for labeling, storing and shipping the tissue samples will be

provided to each investigational center prior to the initiation of subject enrollment.

The investigator will manage the excision wounds following her/his standard of care. All

therapies associated with the care for the excision wounds (e.g., local anesthesia, topical

antibiotics, etc.) must be reported as Concomitant Therapies but their use does not need to be

reported as an AE. If an unexpected event that is not normally associated with the excision

procedure occurs (e.g., infection, an event that is out of the ordinary in severity or duration) it

must be reported as an AE, and any associated therapy must be reported as a Concomitant

Therapy.

At Visit 6, the investigator will see the subject for follow-up on the excision wound care.

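### Target tumors are allowed on the fingers and back of the hand, where the hand-wash step and the 6-hour no-wash rule cannot both be followed

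*Combined protocol and SAP*

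**What the plan says.** All references are to the combined protocol and SAP unless stated.

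- **Site.** Section 5.3 calls for "5 Target cNF Tumors with 1 tumor on the face and 4 tumors on the anterior trunk or upper extremities", and its definition of the upper extremities is "Arms from the shoulders to the tips of the fingers, including the back of the hands but excluding the palms". Fingers and the back of the hand are therefore named as eligible. Section 5.3 also requires that a tumor "Is not in an area subject to repeated trauma"; its examples (shaved skin, beltline, bra strap) do not mention hands.
- **Application.** In Section 4.12.8 the subject should "Gently rub in the study medication until no visible accumulation is evident" and then "Wash her/his hands after completing the application".
- **No-wash rule.** Section 4.12.8 says that after an application a subject should not "Wash or submerse any Target cNF Tumor for at least 6 hours". Section 4.10 lists the rule among things that subjects must do: "Not wash or submerge a Target cNF Tumor for at least 6 hours after a study medication application".
- **Primary reading.** Under Section 6.3.3 the tumors are excised "4 (±1) hours after the Application Completion Time for the last study medication application". Section 8.3.3 averages p-ERK over the five Target tumors of each subject for the primary ANOVA and adds a second ANOVA on within-subject medians. Tumor volume is analyzed in the same way.

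**The concern.** A subject with a Target tumor on a finger or the back of the hand receives two instructions that collide at every dose. Nothing in Sections 4.10, 4.12.8 or 5.3 says what to do. Sites must also confirm at Visits 3 to 5 that all study instructions were followed, which they cannot do cleanly for such a subject.

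The primary endpoint is exposed because the Visit 5 dose is also followed by the hand-wash step, and excision comes 3 to 5 hours later, inside the 6-hour window. If washing removes drug effect, that tumor still enters the within-subject mean with weight 1/5 as though fully treated, and the active arm may look more like vehicle. No exclusion covers this case. The amended Section 8.3.3 allows tumors to be left out of sensitivity analyses only when histology shows that they are not qualifying neurofibromas.

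**Working it through.** **1. Do the instructions conflict?** Take a Target tumor on a finger.

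| Instruction | Section | Force | Effect on a finger tumor |
|---|---|---|---|
| Hands washed after application | 4.12.8 | *should* | Tumor is washed at once |
| Target tumor not washed for 6 hours | 4.12.8 | *should not* | Tumor must stay unwashed |
| Target tumor not washed for 6 hours | 4.10 | *must* | Tumor must stay unwashed |

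Both cannot be obeyed literally. On the back of the hand the same holds if that surface is washed. Neither section makes an exception.

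**2. How much could the primary mean move?** The documents give no figure to reproduce: no expected number of hand tumors, no loss from washing, and no effect size, SD, alpha or power. What follows is illustration.

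Inputs:
- *h*, hand tumors per affected subject: 0 to 4, because the fifth Target tumor is on the face (Section 5.3)
- weight per tumor: 1/5 (Section 8.3.3)
- *f*, share of an arm's subjects affected: assumed
- *w*, share of a hand tumor's drug effect lost: assumed

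If every tumor would otherwise show the same effect Δ, an affected subject's mean effect is Δ(1 − *hw*/5), and the arm's is Δ(1 − *fhw*/5). The attenuation is *f* × (*h*/5) × *w*.

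| *f* (with *h* = 1) | Whole effect lost (*w* = 1) | Half lost (*w* = 0.5) |
|---|---|---|
| 0 | 0 | 0 |
| 10% | 0.10 × 1/5 = 2% | 1% |
| 25% | 0.25 × 1/5 = 5% | 2.5% |
| 50% | 0.50 × 1/5 = 10% | 5% |

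With 12 subjects per arm there are 12 × 5 = 60 Target tumors, so *f* = 10% is 1.2 subjects, or about one tumor in 60. The formal ceiling (*f* = 1, *h* = 4, *w* = 1) is 80%, but nothing in the documents suggests it.

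**3. What would that cost in power?** Assume 12 per arm, two-sided 5%, an unchanged SD, and a true effect of 1.144 SD, which gives 80% power with no dilution. Then 1.144/√(2/12) = 2.80, and power = Φ(2.80*k* − 1.96), where *k* is the share of effect kept.

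| *k* | Power |
|---|---|
| 1.00 | 80% |
| 0.98 | 78.4% |
| 0.95 | 75.9% |
| 0.90 | 71.3% |

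Section 4.1 plans about 56 subjects (14 per arm), against 48 elsewhere. The attenuation does not depend on this, and the powers are the same if the effect is reset to give 80% at 14 per arm.

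**4. Does the median analysis protect?** With one affected tumor, the median of five stays between the two middle values of the other four. With two affected, it can reach the most extreme of the remaining three. With three or more, an affected tumor can itself be the median. Protection is good for one tumor and weakens after that, and this is a second analysis, not the primary one.

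**The case against.** The best case against the point is that the conflict is narrow and its consequence unproven. Most of that stands, and it rules out several stronger readings that a reader might infer.

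- *Subjects must wash their hands.* Section 4.12.8 says *should*. The *must*, in Section 4.10, attaches to leaving the tumor unwashed, and Section 4.10 does not list the hand wash at all.
- *A hand tumor cannot be treated.* The gel is rubbed in until none is visible before the wash, and a tumor on the back of the hand might be kept out of it. Staff observe technique at Visit 2, and the Visit 5 dose is applied at the center. What cannot be done is to follow both instructions as written.
- *The p-ERK result is diluted.* Hand sites are permitted, not required. Dilution needs hand tumors to be chosen in the active arms and drug effect to be lost by washing after rub-in. The documents show neither.
- *Variance rises in the active arms only.* Section 3.2 expects application of a gel to have an effect on treated tumors, so washing off vehicle could matter too.

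It can also be said that the repeated-trauma list is open-ended and might be used to exclude hands. That carries little weight, because Section 5.3 names them as eligible. Finally, the study is exploratory and sized on practical grounds, so a loss of a few percent would not overturn its purpose. That is a reason for low severity, but the instructions still contradict each other.

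**Conclusion.** The contradiction among Sections 4.10, 4.12.8 and 5.3 is in the current text and needs reconciling. Dilution of the primary p-ERK mean is possible, not shown. Its size runs from zero with no hand tumors to about 1% to 5% of the arm's mean effect if 10% to 25% of subjects have one hand tumor and half to all of its effect is lost. It reaches 10% if half the subjects are affected with full loss. These figures rest on assumed frequencies and losses, and on an equal effect across tumors. The planned median ANOVA protects only in part. Low severity, but cheap to remove.

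**What to change.** Reconcile Sections 4.10, 4.12.8 and 5.3. The simplest way is in Section 5.3: for the five Target tumors only, end the upper-extremity region at the wrist and change the body chart to match. The application instructions can then stay as they are. The Untreated tumor receives no gel, so the wash conflict gives no reason to change its region. Clarifying the instructions for hand tumors would also remove the conflict; that choice is the sponsor's.

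If any hand Target tumor is already enrolled, prespecify before unblinding a sensitivity analysis of p-ERK and volume that leaves it out and averages the subject's remaining Target tumors. Report the number of such tumors by arm. Section 5.3 already records locations on body charts and in the CRFs, so no new data are needed.

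The cost is one amended definition and the loss of a few otherwise eligible hand tumors; the rest of the arm and the anterior trunk stay available. In the sensitivity analysis, a mean of four tumors instead of five raises the within-subject part of its variance by a factor of 5/4 for the affected subjects.
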